2. SUBJECT POPULATION

2.1. Population Definitions

The following subject populations will be evaluated and used for presentation and analysis of the data:

- All Subjects as Treated (ASaT) Population: All subjects who received a partial or full dose of 1 single study injection, excluding subjects who have no on-study safety data. The subjects will be analyzed according to treatment received in case of a treatment error.
- Per-Protocol (PP) Population: All randomized subjects who received the vaccine dose to which they were randomized, have PHV01 IgG ELISA titer or PsVNA results on Days 1 (baseline) and 29 (± 5 days), and do not have any protocol violations that influence interpretation of immunogenicity endpoints.
- Modified Intent-to-Treat (mITT) Population: All randomized subjects who received a single study injection and have at least 1 post-injection immunogenicity evaluation. The subjects will be analyzed according to treatment received in case of a treatment error.

The ASaT population is the primary population for the analysis of safety endpoints. The PP population is the primary population for the analysis of immunogenicity parameters. The mITT population may be used for additional analyses of immunogenicity endpoints, should there be a 10% difference or more in the sizes of the mITT and PP analysis sets (see Section 4.3). Intervals for analysis, i.e., visit windows, are further defined in the Schedule of Events.

2.2. Protocol Violations

At the discretion of the Sponsor, major protocol violations, as determined by a review of the data prior to unblinding of the study results and the conduct of statistical analyses, may result in the exclusion of a subject's data from the PP population. Veristat will be responsible for producing the final protocol violation file (formatted as a Microsoft Excel file), in collaboration with the Sponsor and the data monitoring group as applicable; this file will include a description of the protocol violation and clearly identify whether this violation warrants exclusion from the PP population. The decisions on PP exclusions will be finalized prior to interim analysis and the complete file of protocol violations will be finalized prior to final database lock for CSR.

All protocol violations will be presented in a data listing.

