3.3. MEASURES TAKEN TO MINIMIZE/AVOID BIAS

3.3.1. Randomization

This is a single-blind study, with group assignment hidden from site staff (apart from the compounding pharmacist) and subjects, along with a blinded CRA who will monitor the site records. To further avoid the potential for bias, the Medical Monitors (Sponsor and CRO) will remain blinded as well, until the database is frozen for the interim analysis (IA). Randomization will be stratified to achieve balance of sex across PHV01 dose levels and placebo recipients. For each randomization number, 2 replacement subject randomization numbers will be generated. The treatment assignment for replacement subjects will be the same as the subject who is being replaced.

Study personnel will obtain treatment identification (ID) numbers from the Interactive Web Response System (IWRS) as eligible subjects, who have successfully completed the screening process and are deemed eligible to participate by the PI (or another designated Investigator), are enrolled and proceed to vaccination.

Care will be taken to ensure that recruiting and screening processes are unbiased with regard to race and gender. To maintain randomization, alternates will be used, if necessary, in the order in which they were deemed eligible. Alternates are allowed to join the next cohort if they still meet entry criteria.

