3.3.2. Blinding and Unblinding

Dosing materials will be prepared by an unblinded study pharmacist, labeled with the subject identifier, and administered by a member of the study team. All dosing materials will have identical appearance and all members of the site study team (apart from the unblinded pharmacist) will be blinded to the treatment assignment, along with the study participants. Apart from the individuals noted above, the Sponsor and CRO personnel will be unblinded, although the blind will be maintained during discussions with the site PI and staff. Subjects and Investigators will remain blinded to the subject's group assignment (PHV01 dose or placebo) until the study database is locked.

Interim Analysis of Safety and of Immunogenicity

One IA will be performed when all 36 subjects have completed the day 29 follow-up. For this IA, the records to be included from each subject will be 'frozen' after being monitored and queries will be resolved without unblinding the site staff. Pre-specified tables, listings, and figures will describe solicited local and systemic AEs, unsolicited AEs, and any MAAEs or SAEs, along with a simple listing of labs by subject without analysis of the latter.

For immunogenicity analyses, tables, listings, and figures will describe the serum IgG ELISA and PsVNA for each Group. In addition, RT-qPCR results from plasma, urine, and saliva samples will be used to assess viremia and shedding. Details regarding the IA for safety, immunogenicity, and sample algorithms will be provided in the Statistical Analysis Plan (SAP).

Individual Subject Unblinding

The group assignment for an individual subject may be unblinded during the course of the study if the PI deems that, for health purposes, the blind must be broken emergently to evaluate an AE;

the other SRC members should be included in the decision if time allows. Only in the case of an emergency, when knowledge of whether the subject has received the IP is essential for the clinical management or welfare of the subject, may the unblinded study pharmacist unblind that subject's treatment assignment. Unblinding at the study site for any other reason other than to confirm rVSV shedding positivity will be considered a protocol violation and reported as a major deviation.

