3.8. TRIAL TREATMENT RANDOMIZATION CODES

A single document delineating the randomized assignment of treatment ID numbers (according to the methodology outlined in Section 3.3.1) to subjects will be generated and maintained in a secure location as part of the regulatory file. During the study, the unblinded site pharmacist, representatives of the Sponsor, and applicable regulatory authorities will have access to this list if required by their duties.

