7. STATISTICAL METHODS

An SAP, providing details about the specific planned analyses and statistical tests, will be prepared and approved by the Sponsor and its designees prior to study database lock and unblinding of the single-blind subject treatment assignments.

For safety and immunogenicity endpoints, tests will be performed comparing each dose level to the placebo group. Additional tests may be performed between dose levels to determine dose response. All statistical tests will be performed at the 2-sided 5% level of significance. No adjustments for multiple testing will be considered. No imputations will be made for missing immunogenicity data.

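### Judgement-based exclusions from the primary immunogenicity population rest with Sponsor and CRO staff whom the protocol makes unblinded, and under the SAP up to three of them need no mITT check

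*SAP*

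**What the plan says.** **Who decides, and when.** SAP 2.2: "At the discretion of the Sponsor, major protocol violations, as determined by a review of the data prior to unblinding of the study results" (the sentence goes on to require that the review also precede the statistical analyses) may lead to exclusion from PP. The CRO builds the violation file and marks which violations exclude, "in collaboration with the Sponsor and the data monitoring group as applicable". On timing: "The decisions on PP exclusions will be finalized prior to interim analysis".

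**Who is blinded.** Protocol 3.3.2: "Apart from the individuals noted above, the Sponsor and CRO personnel will be unblinded". The exceptions come from Protocol 3.3.1: a CRA who monitors site records, and the Sponsor and CRO Medical Monitors, who stay blinded until the database is frozen for the interim analysis. Protocol 3.8 adds that during the study "representatives of the Sponsor, and applicable regulatory authorities will have access to this list if required by their duties". Protocol 5.1.5 keeps the code from the assay laboratory.

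**What PP requires.** Under SAP 2.1 a subject must have received the assigned dose, must "have PHV01 IgG ELISA titer or PsVNA results on Days 1 (baseline) and 29" (within 5 days), and must have no violation that affects interpretation of the immunogenicity endpoints. Neither document lists such violations.

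**When mITT is shown.** Protocol 7.3 makes it unconditional. Protocol 7.5.2 makes it optional. SAP 2.1 makes it optional when the two sets differ in size by 10% or more. SAP 4.3 makes it mandatory when more than 10% are excluded from PP.

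**The concern.** The usual protection for a per-protocol set is that the people who apply a judgement criterion do not know the treatment group or the outcome. SAP 2.2 seeks that protection through timing: the list closes before results are unblinded and before the interim analysis. Timing cannot blind people who already hold individual assignments, and Protocol 3.3.2 puts most Sponsor and CRO staff in that position.

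The criterion leaves room for choice. Protocol 5.2 restricts oral and injected corticosteroids through Day 29 and also places no limit on rescue medication. A steroid given for a post-dose reaction could therefore be called an excluding violation or not, and either call could be defended.

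The stake is the Day 29 comparison by group. SAP 3.12 says the interim analysis is to guide dose selection for the next trial, and the PP set is primary for its immunogenicity results. With ten subjects per dose, each one counts. If a few were removed, the SAP would not oblige anyone to show the result with them included.

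**Working it through.** **1. The plan's own figure.** Inputs from Protocol 7.1 and SAP 3.1: geometric SD 3.3 (carried over from the Ebola vaccine), 10 vaccinees against 6 placebo, two-sided alpha 0.05.
- Noncentrality = ln(6.4) / [ln(3.3) × √(1/10 + 1/6)] = 1.856 / (1.194 × 0.516) = 3.01, on 14 degrees of freedom.
- Power by the noncentral t is 79.9% at 6.4-fold and 90.0% at 8.6-fold. The stated 80% and 90% are reproduced, so 3.3 is the right SD to use below.

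**2. Is the decision blind?**
- The decision belongs to the Sponsor, with the CRO preparing the file (SAP 2.2).
- Sponsor and CRO personnel are unblinded except the CRA and the Medical Monitors (Protocol 3.3.1 and 3.3.2).
- The decision is not assigned to the CRA or the Medical Monitors in either document.
- Protocol 7 requires the SAP to be approved "prior to study database lock and unblinding of the single-blind subject treatment assignments". That points to a later unblinding. It fits the site and the subjects, but not the Sponsor staff described in 3.3.2.
- Final PP membership needs Day 29 results to exist, so it cannot close before the assays report. This requires knowing that a result exists, not its value. Neither document says whether the deciders see the values.

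**3. When is mITT required?** Take 36 subjects as the denominator; SAP 4.3 does not name one.

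| Excluded | Share of 36 | SAP 2.1 (10% or more, optional) | SAP 4.3 (over 10%, mandatory) |
|---|---|---|---|
| 1 | 2.8% | not met | not met |
| 2 | 5.6% | not met | not met |
| 3 | 8.3% | not met | not met |
| 4 | 11.1% | met | met |

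The pattern is the same for any denominator from 31 to 39, the latter allowing for three replacements. Losses for other reasons, such as a missing Day 29 result, count toward the same 10%. The threshold is on the total, so three exclusions could be 3/10 = 30% of one dose group or 3/6 = 50% of placebo.

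The two SAP rules can also disagree, in a corner case. Suppose four subjects are out of PP, one of them because there is no post-dose sample. SAP 4.3 gives 4/36 = 11.1% (run). SAP 2.1 compares 35 with 32, and 3/35 = 8.6% (not triggered).

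**4. How far could a GMT move?** The documents give no exclusion rate and no link between exclusion and titer, so these are bounds, not forecasts.
- Exclusion unrelated to titer: expected shift 1.00-fold, for any number excluded.
- Upper bound, the lowest titers of ten removed. Normal order statistics for n = 10 put the three lowest at 1.539, 1.001 and 0.656 SD below the mean.
 - One removed: 1.539/9 = 0.171 SD, and 3.3^0.171 = 1.23-fold.
 - Three removed: (1.539 + 1.001 + 0.656)/7 = 0.4566 SD, and 3.3^0.4566 = 1.72-fold (1.73 if the exponent is first rounded to 0.457).
- If three violators of ten are unrelated to titer, the chance that they happen to be the three lowest is 1/C(10,3) = 1/120 = 0.8%.

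**The case against.** The strongest reply has four parts.

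- **There are real limits on discretion.** An exclusion needs a major violation, described in a file, that bears on immunogenicity. It must be settled before any analysis. Low titer is not a ground. Access to the list under Protocol 3.8 applies only where duties require it. Protocol 7.2 refers to an Unblinding Plan that may say who holds codes and results. All of this stands, and it narrows the room for bias. It does not make the deciders blind.
- **The protocol already promises mITT.** Protocol 7.3 does so without a threshold. This stands too, so the gap belongs to the SAP rules. But Protocol 7.5.2 is optional, and the SAP governs the tables that are produced.
- **Exclusions would be visible.** SAP 4.1 tabulates the size of each population and SAP 2.2 lists every violation, so a careful reader could find the subjects. The by-group result with them included is still not assured.
- **This is a small, largely descriptive Phase 1 trial.** SAP 3.1 says the sample size was not set for formal testing, and SAP 3.7 combines statistical and clinical judgement. That is a fair reason to keep the point modest.

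A reader might infer that the Sponsor will see titers and choose exclusions by them, or that the Phase 2 dose will be distorted. The documents do not support either. Access to titers could only be inferred from silence. No text describes selection by titer. Nothing says that the dose with the highest GMT is carried forward: Protocol 7.2 also brings in safety, seroconversion and distribution curves, and Protocol 1.3 asks for the lower dose limit.

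**Conclusion.** The point holds as a weakness in procedure. The stated safeguard in SAP 2.2 does not make PP exclusions blind, because the Sponsor and CRO roles it relies on are mostly unblinded under Protocol 3.3.2 and the blinded exceptions are not given the task. The cross-check is described four ways, and under the SAP it is not required for one to three exclusions of 36.

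The expected size is zero if exclusions are unrelated to titer. The upper bound for one dose group is about 1.23-fold for one exclusion and 1.72-fold for three, assuming log-normal titers, geometric SD 3.3, ten subjects, and removal of exactly the lowest values. Nothing in the documents predicts that pattern. Two things could soften the conclusion: an Unblinding Plan that already restricts who decides, and a choice to run mITT anyway, which neither document forbids. The change is worth making because it is cheap and removes the question.

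**What to change.** **SAP 2.2.** State that the Medical Monitors decide and sign all violation-based PP exclusions before the interim freeze, while Protocol 3.3.1 still keeps them blinded, from a violation file that carries neither group assignment nor titer values. The timing condition matters, because their blinding ends at the freeze. Exclusions for a missing Day 1 or Day 29 result are then applied mechanically once the assays report, with no judgement involved.

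**SAP 2.1 and 4.3.** Replace both thresholds with one rule that follows Protocol 7.3: present Day 29 GMT and seroconversion by group in mITT whenever PP and mITT differ. This also satisfies the optional wording of Protocol 7.5.2.

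**Cost.** One extra sign-off and, at most, one repeated Day 29 table. The design, sample size and primary population are unchanged, and no new staff are needed.

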3. GENERAL STATISTICAL METHODS

3.1. Sample Size Justification

The sample size for this Phase 1 study (N=36 subjects; total N=10 per vaccine dose level [30 vaccinees and 6 placebo]) was selected to provide initial data and obtain estimates of safety and immunogenicity parameters and their respective variabilities. Group size is based on prior experience with ERVEBO safety studies and assumptions from the responses seen in the preclinical studies. This Phase I study is therefore designed with the goal of providing further information for better planning of future in-human studies. As this is a FIH study of PHV01, the sample size was established to provide reasonable information for descriptive purposes and not specifically designed for formal hypothesis testing.

Safety: With a sample size of 10 subjects, an upper bound of 30.9% is established for the 2-sided 95% confidence interval (CI) for the incidence of an AE in the case that the event is not observed according to the two-sided 95% (Clopper-Pearson) exact CI. Alternatively, when pooled together all 30 vaccinees, an upper bound of 11.6% is provided. This established the sample sizes needed to ensure minimal AE rates could be detected with confidence.

Immunogenicity: Clinical data for the rVSV-ZEBOV-GP Ebola vaccine showed that a dose of 3×10^6 pfu/mL yielded a Day 29 GMT IgG ELISA titer of 1400 EU/mL and geometric standard deviation (SD) of 3.3. Assuming that the variability in responses to PHV01 is similar, the proposed group sizes afford 80% (alternate 90%) power to detect a 6.4-fold (alternate 8.6-fold) increase, comparing geometric mean ELISA titer using a two-sided test with alpha=0.05 for each vaccine group with the placebo group. Alternatively, performing the same comparison against placebo by pooling all three treatment groups with a total 30 vaccinated subjects, we would have 4.7-fold and an alternate 5.9-fold with 80% and 90% power, respectively.

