7.1. PLANNED ENROLLMENT AND REASON FOR SAMPLE SIZE

This is a Phase 1 study, where both descriptive and inferential statistical methods will be used to fully explore the preliminary data for planning of future studies and will define future study endpoints. This study is intended to provide initial safety, tolerability, and immunogenicity data for the vaccine candidate. In addition, immunogenicity endpoints will be evaluated for the potential of a dose-response relationship to increasing doses of the IP, including placebo as a 0-dose level.

The sample size for this Phase 1 study (N=36 subjects total: N=10 per vaccine dose level (30 vaccinees) and 6 placebo) was selected to provide initial data to obtain estimates of safety and immunogenicity parameters and their respective variabilities. Group size is based on prior experience with ERVEBO safety studies and assumptions from the responses seen in the preclinical studies. This Phase I study is therefore designed with the goal of providing further information for better planning of future in-human studies. As this is a FIH study of PHV01, no current human data exist to substantiate power or treatment effect estimates.

Safety: With a sample size of 10 subjects, an upper bound of 30.9% is established for the two-sided 95% confidence interval for the incidence of an AE in the case that the event is not observed according to the two-sided 95% (Clopper-Pearson) exact confidence interval.

Immunogenicity: Clinical data for the rVSV-ZEBOV-GP Ebola vaccine showed that a dose of 3x10⁶ pfu/mL yielded a day 29 GMT IgG ELISA titer of 1400 EU/mL and geometric standard deviation of 3.3. Assuming that the variability in responses to PHV01 is similar, the proposed group sizes afford 80% (alternate 90%) power to detect a 6.4-fold (alternate 8.6-fold) increase, comparing geometric mean ELISA titer using a two-sided test with alpha=0.05 for each vaccine group with the placebo group. Alternatively, performing the same comparison against placebo by pooling all three treatment groups with a total 30 vaccinated subjects, we would have 4.7-fold and an alternate 5.9-fold with 80% and 90% power, respectively.

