4.3. Immunogenicity Evaluation

Immunogenicity analyses will be conducted using the PP population. Supportive analyses of immunogenicity will be based on the mITT population if the number of subjects excluded from PP population is more than 10%.

4.3.1. Geometric Mean Titers and Mean Fold Increase of IgG ELISA Antibody and Neutralizing Antibody PsVNT

For IgG ELISA antibody titers and neutralizing antibody titers PsVNT (PsVNT₅₀ and PsVNT₈₀), GMT, and 95% confidence limit will be provided on Days 1, 8 (if tested), 15, 29, 85, and 181, where the GMT is calculated as the anti-log of the base-2 log transformed mean and the same for the corresponding confidence limit. Results will be presented by treatment group along with a combined PHV01 group, and the descriptive statistics will include the GMT, the geometric standard deviation, 25th percentile, median, 75th percentile, minimum, and maximum values. If appropriate, the analyses will be repeated for the GMT using the anti-log of the base-10 log transformed mean.

Pairwise comparison of the above antibody titer levels for each PHV01 dose level to one another and to the placebo group, as well as the comparison of the combined PHV01 dose group relative to the placebo group will be performed with Satterthwaite t-tests. T-tests will be performed on log-2 transformed values and the resulting estimated mean difference and associated 95% CI will then be back transformed using base-2 antilogarithms to obtain estimates

on the ratio scale. If appropriate, the analyses will be repeated using base-10 log transformed values and back transformed using base-10 antilogarithms to obtain estimates. In the event of extreme outliers or non normally distributed data, Wilcoxon rank-sum test may be performed to support the comparison.

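### The stated detectable fold-increases belong to an equal-variance t-test; with the planned Satterthwaite test and the same inputs, the combined-vaccine comparison has 70% power, not 80%

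*SAP*

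**What the plan says.** SAP 3.1 sets the group sizes ("total N=10 per vaccine dose level [30 vaccinees and 6 placebo") and takes a "geometric standard deviation (SD) of 3.3" from data on the related Ebola vaccine, "Assuming that the variability in responses to PHV01 is similar". From this it concludes that the groups "afford 80% (alternate 90%) power to detect a 6.4-fold (alternate 8.6-fold) increase" when each dose is tested against placebo, two-sided at 0.05. For the combined group it adds that "by pooling all three treatment groups with a total 30 vaccinated subjects, we would have 4.7-fold and an alternate 5.9-fold", again for 80% and 90%. Protocol 7.1 gives the same four figures: "the proposed group sizes afford 80% (alternate 90%) power to detect a 6.4-fold (alternate 8.6-fold) increase" for a single dose, and 4.7-fold and 5.9-fold for the pooled vaccinees. Neither section says which form of two-sample test the figures refer to, and neither gives a GSD for placebo.

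SAP 4.3.1 does name the test. Each dose is compared with placebo and with the other doses on log-2 titers, and the "comparison of the combined PHV01 dose group relative to the placebo group will be performed with Satterthwaite t-tests". Satterthwaite tests are used again for the fold-rise ratios. The same section adds an ANOVA across the dose levels and placebo, with Tukey comparisons if the F-test is significant; no combined-vaccine contrast is listed for it. SAP 3.2 commits to formal two-sided tests at 0.05 on the primary and secondary immunogenicity endpoints.

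**The concern.** A power statement should describe the test that will be run. With equal variances and balanced arms, the equal-variance and Satterthwaite tests have similar power, so the choice matters little. Here the arms are unbalanced, 30 to 6 in the combined comparison. The equal-variance test borrows the variance estimate from the 30 vaccinees and works on 34 degrees of freedom. The Satterthwaite test may not borrow it. It must rely on 6 placebo values for most of its standard error.

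What is at stake is how the combined comparison is read. SAP 3.1 offers pooling as a way to bring the detectable fold at 80% power down from 6.4 to 4.7. If the planned test does not deliver that, a reader of the interim or final results will overrate what a non-significant combined comparison excludes.

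**Working it through.** **Inputs.** From SAP 3.1: two-sided alpha 0.05; GSD 3.3; 10 per dose, 30 vaccinees combined, 6 placebo. From SAP 4.3.1: t-test on log titers. The log base cancels, so natural logs are used: SD = ln 3.3 = 1.194. Assumption: the same SD in placebo, which the text does not state but which step 1 shows is what generates the plan's figures.

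**Step 1: reproduce the plan's figures.** Equal-variance t-test, df = n1 + n2 − 2, noncentrality = ln(fold) / [SD × √(1/n1 + 1/n2)].

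- 10 v 6: standard error 1.194 × √(1/10 + 1/6) = 0.617; df 14. Noncentrality at 6.4-fold is 1.856/0.617 = 3.01, giving 79.9% power; 8.6-fold gives 90.0%.
- 30 v 6: standard error 1.194 × √(1/30 + 1/6) = 0.534; df 34. Noncentrality at 4.7-fold is 1.548/0.534 = 2.90, giving 80.4% power; 5.9-fold gives 89.8%.

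Solving for the fold at 80% and 90% gives 6.41 and 8.59 (10 v 6), and 4.66 and 5.94 (30 v 6). All four stated values match after rounding. Two other routes were tried and do not match: a normal approximation (5.63, 7.38, 4.46, 5.64) and a one-sided t-test (5.02, 6.68, 3.88, 4.93).

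**Step 2: what the Satterthwaite test has to work with.** With equal SDs the common variance cancels:

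df = (1/n1 + 1/n2)² / [(1/n1)²/(n1 − 1) + (1/n2)²/(n2 − 1)]

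- 10 v 6: 0.0711 / (0.00111 + 0.00556) = 10.7, against 14.
- 30 v 6: 0.0400 / (0.00004 + 0.00556) = 7.15, against 34.

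At 30 v 6 the placebo arm supplies (1/6)/(1/6 + 1/30) = 83% of the variance of the difference.

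**Step 3: power of the planned test at the stated folds.** Simulation (2,000,000 replicates), with a noncentral-t approximation at the df above as a cross-check:

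| Comparison | Fold | Stated power | Satterthwaite, simulated | Satterthwaite, approximate |
|---|---|---|---|---|
| 10 v 6 | 6.4 | 80% | 77.1% | 78.0% |
| 10 v 6 | 8.6 | 90% | 87.8% | 88.5% |
| 30 v 6 | 4.7 | 80% | 70.3% | 70.5% |
| 30 v 6 | 5.9 | 90% | 81.0% | 81.5% |

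The simulated type I error of the Satterthwaite test at 30 v 6 is 5.5%, so the lower power is not the result of a conservative test.

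**Step 4: folds the planned test needs.**

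| Comparison | 80% power, stated | 80%, Satterthwaite | 90% power, stated | 90%, Satterthwaite |
|---|---|---|---|---|
| 10 v 6 | 6.4 | 6.9 | 8.6 | 9.4 |
| 30 v 6 | 4.7 | 5.8 | 5.9 | 7.7 |

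At 80% power, pooling is presented as lowering the detectable fold by 1 − 4.7/6.4 = 27%. Under the planned test it lowers it by 1 − 5.8/6.9 = 16%.

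**Step 5: sensitivity to the placebo GSD.** Vaccine GSD held at 3.3; Satterthwaite power at 4.7-fold, 30 v 6:

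| Placebo GSD | 3.3 | 3.0 | 2.8 | 2.5 | 2.0 |
|---|---|---|---|---|---|
| Power | 70% | 76% | 81% | 88% | 97% |

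**Side check.** The Tukey comparison of one dose with placebo (four groups, 36 − 4 = 32 df, GSD 3.3) has 62% power at 6.4-fold. SAP 3.1 does not attribute its power to that analysis, so this does not add to the discrepancy, but it does not support the stated figures either.

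**The case against.** The strongest reply is that equal variability is an inference. SAP 3.1 carries the Ebola-vaccine GSD over to responses to PHV01 and is silent on placebo. Placebo titers may well vary less: people with previous filovirus vaccination or potential filovirus contact are excluded (Protocol 4.5), and SAP 1.2.5.2 assigns a fixed value to ELISA results below the limit of detection, so placebo subjects who all stay below it would have identical values. With a placebo GSD of about 2.8 or less, the Satterthwaite test reaches the stated 80% and 90%. This stands as a limit on the 70%. It does not rescue the text, because the stated folds were produced with 3.3 in both arms. A lower placebo spread is also not assured: values split between the below-detection value and half the quantitation limit could widen it, and that limit is not given.

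Second, the sample size is described as chosen for descriptive purposes, Protocol 7.1 says that no human data exist to support power estimates, and GMT ratios with confidence intervals will be reported in any case. This limits the weight of the point. But the same sections go on to give four numerical power claims, and SAP 3.2 plans formal tests.

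Third, for a single dose against placebo the loss is only 2 to 3 percentage points. That is correct; the material error is in the combined comparison.

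**Conclusion.** The concern holds. The stated folds are equal-variance figures, and the test named in SAP 4.3.1 does not deliver the stated power on the inputs that produce them. The shortfall is about 10 points for the combined comparison (70% for 80%, 81% for 90%) and 2 to 3 points for each single dose. These sizes rest on log-normal titers, GSD 3.3 in both arms and no loss of subjects. If the placebo GSD is appreciably lower, the planned test does better than stated. Either way, the text as written neither matches the planned test nor states the assumption that decides the answer. It should be corrected, but it does not call the design or the sample size into question.

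**What to change.** In SAP 3.1, restate the detectable folds for the Satterthwaite test at 80% and 90% power: 6.9 and 9.4 for each dose against placebo, and 5.8 and 7.7 for the combined group. State that GSD 3.3 is assumed in both arms. Add one line for a smaller placebo GSD; at 2.0, for example, power at 4.7-fold in the combined comparison is 97%. Protocol 7.1 carries the same figures and should be brought into line.

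The cost is wording. The headline figures become somewhat less favourable, and the protocol text has to go through the sponsor's change procedure. Sample size, data collection and planned analyses stay as they are.
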